10.8.2 Bailout

Bailout procedures should be avoided unless required for subject safety. If bailout procedures are performed, justification should be documented on the CRF.

If a subject in this study experiences a major dissection or an occlusive complication (as evidenced by decreased target vessel flow, chest pain, or ischemic electrocardiogram (ECG) changes which do not respond to standard rescue techniques), bailout procedures may be performed. For these events occurring during the study procedure, additional stenting with study stents may be employed as a bailout treatment.

In this study, the target lesion(s) is/are to be selected with the intent to cover each lesion with a single stent. If incomplete coverage occurs during the procedure, additional stenting with study stents may be employed to provide complete coverage.

It is recommended to overlap the Resolute Onyx stents 1-2 mm to avoid the potential for gap restenosis.

10.8.3 Staged procedures

Treatment of all target lesions with the Resolute Onyx stent(s) within a single PCI procedure is encouraged, if reasonable and safe. However, when staging is required for clinical reasons, it is recommended to perform the staged procedure using Onyx within 6 weeks from the index procedure.

- Staging should be pre-specified at the time of the index procedure
- Staging should not involve a segment directly adjacent to a segment treated during the index PCI
- Every urgent coronary reintervention before the planned staged procedure is considered an event

10.8.4 Treatment Failure

Following subject treatment, study stent(s) that enter the guide catheter and fail to be implanted at the intended location are considered treatment failures and should be recorded in the CRF. Treatment failures should be followed-up for safety purposes through 12 months and will be included in the intent-to-treat (ITT) population.

10.9 Scheduled Follow-up Visits

Refer to section 10.2 Data Collection for the information collected at the follow-up visits.

10.10 Assessment of Efficacy

Assessments of effectiveness will include acute device, lesion, and procedural successes as well as adjudication of any revascularizations reported through each subject's follow-up.

10.11 Assessment of Safety

All serious adverse events and device deficiencies will be evaluated by Medtronic.

The Clinical Events Committee (CEC) will review and adjudicate all clinical events possibly related to study endpoints that need adjudication when the necessary data are available.

10.12 Recording Data

Data collected on each subject will be recorded on a web-based electronic Case Report Form (CRF). This study will utilize an Oracle Clinical Remote Data Capture (RDC) system that is the property of Medtronic. Each enrolled subject is assigned a unique study ID number. Records of the subject/subject ID relationship will be maintained by the study site. Individual subject medical information obtained as a result of this study will be considered confidential.

Authorized site personnel as indicated on the Delegation Task List (DTL) will record required data on electronic case report forms. Study personnel delegated for CRF completion and/or approval per the DTL will be trained on the use of the RDC system and thereafter provided with a user name and password to access the system. Passwords are individual and cannot be shared.

The CRFs must be completed and/or updated to reflect the latest observations on the subjects participating in the study. The investigator (or approved sub-investigator) will electronically sign the appropriate pages of each CRF. The Oracle Clinical RDC system maintains an audit trail of entries, changes, and corrections in CRFs. If a person only authorized to complete CRFs makes changes to an already signed CRF, the investigator shall re-approve this CRF.

The hospital files (electronic or paper) will constitute source data. For the purpose of adjudication of events by the CEC, relevant event-related source documents will be redacted and collected for events that need to be adjudicated by the CEC.

The CRFs may not serve as source documents. Source documentation for data elements not routinely captured in medical records (e.g. angiogram variables, procedural details) may vary from center to center. The site may use technical worksheets if identified as source documents. Worksheets need to be signed and dated by the Principal Investigator or a delegated Investigator.

The Principal Investigator is responsible for ensuring that all sections of each CRF are complete and correct and that those entries can be verified against source data.

Medtronic will be responsible for the processing and quality control of the data. Data review, database cleaning and issuing and resolving data queries will be done according to Medtronic internal SOPs and the Data Management Plan for this study. The study database will employ validation programs (e.g. range and logic checks) on entered data to identify possible data entry errors and to facilitate data validation.

10.13 Deviation Handling

A study deviation is defined as an event where the Investigator or site personnel did not conduct the study according to the Clinical Investigational Plan, applicable laws or regulations, or the Investigator Agreement.

Regulations require that Investigators maintain accurate, complete and current records, including documentation of any deviations from the investigational plan including the date of and reason for the deviation. The deviations must be reported to the sponsor on the CRF.

Investigators are required whenever possible to obtain prior approval from the Medtronic Clinical Research Department before initiating changes in or deviations from the investigational plan, except

where necessary to protect the life or physical well-being of a subject in an emergency. Such approval will be documented in writing and maintained in the study files. Prior approval is not expected in situations where unforeseen circumstances are beyond the Investigator's control (e.g., subject did not attend scheduled follow-up visit, blood sample lost by laboratory, etc.), however, the event, is still considered a deviation.

Deviations shall be reported to Medtronic regardless of whether medically justifiable, pre-approved by Medtronic, or taken to protect the subject in an emergency. Deviations to protect the life or physical well-being of the subject in an emergency must be reported to Medtronic and the IRB/EC within five working days.

Subject-specific deviations will be reported on the non-compliance CRF. Deviations that are not subject-specific (e.g. unauthorized use of an investigational device outside the study, unauthorized use of an investigational device by a physician who has not signed an Investigator Agreement, etc.) will be reported to Medtronic in writing. Investigators will also adhere to procedures for reporting study deviations to their IRB/EC in accordance with their IRB/EC requirements.

The investigational site's compliance with the clinical investigational plan will be assessed on an ongoing basis. Corrective and preventive action plans will be developed and implemented to secure compliance. In case of serious noncompliance, the sponsor may decide to stop subject enrollment at an investigational site based on its assessment.

10.14 Subject Exit, Withdrawal or Discontinuation

A study subject has the right to discontinue participation in the study at any time without penalty or loss of benefits to which the subject is otherwise entitled. A withdrawn subject will be treated according to standard of medical care and will not be replaced. Subjects will be included in the analyses up to the time that consent was withdrawn.

If a subject decides to withdraw from the study, the investigator will document the reason for withdrawal and indicate any rationale for the withdrawal from the study in the subject's file. Subjects will be followed up per standard of care in case problems related to device safety or performance occur, if applicable. Subjects may decide to withdraw from study follow up visits/contacts but consent to continue to allow data collection from their medical records.

10.14.1 Study Exit

A study exit eCRF is required for all subjects. Prior to exiting a subject from the study, it is recommended to follow the subject until all ongoing system and/or procedure related AEs are resolved or unresolved with no further actions planned. Following exit, subjects will continue to receive standard medical care. Upon exiting from the study, no further study data will be collected, or study visits will occur for the subject. All data available through the time of the subject's exit will be used for analysis.

Subjects are urged to remain in the study as long as possible but may be exited from the study for any of the following situations:

- Study completed
- Subject lost to follow-up
- Subject death
- Subject did not meet inclusion/exclusion criteria
- Subject was not implanted with a (investigational) device
- Subject did not provide consent

- Subject chooses to withdraw (e.g., consent withdrawal, relocation to another geographic location)
- Investigator deems withdrawal necessary (e.g., medically justified, inclusion/exclusion criteria not met, failure of subject to maintain adequate study compliance)

The following information is required to be collected at study exit:

- Reason for exit

If discontinuation is because of safety or lack of effectiveness, the subject shall be asked to be followed for collecting safety data outside the clinical investigation.

10.14.2 **Study Completed**

At the completion of the 36-month follow-up visit, subjects will be exited from the study. The 36-month follow-up visit and exit visit should be combined, and both a 36-month follow-up CRF and a Study Exit CRF need to be completed.

10.14.3 **Lost to Follow-up**

Subject Lost-To-Follow-Up (LTFU) should be avoided as much as possible and investigators are urged to do their utmost best to maintain subject follow-up compliance. Contacting the subject's general practitioner or referring cardiologist should be considered in case the subject cannot be reached in order to obtain information about the subject's health status and documented in the subject's file. Continuous attempts (phone, email, certified letter etc.) throughout the 36-month follow-up period should be made to contact the subject, the subject's family or referring physician before documenting a subject LTFU (at least three documented attempts must be made). It is recommended that death study databases (SSDI) should be checked before subjects are considered LTFU. A subject is not considered LTFU until the subject's 36-month follow-up window has closed. Once a subject has completed their 36-month follow up visit, a study exit form must be completed.

10.14.4 **Subject Chooses to Exit (i.e. Revokes Consent)**

A subject can withdraw from the study at any time. If the subject wishes to exit from the study (i.e. the subject revokes consent), the study site is required to document the reason for exit on the Exit CRF. In addition, study sites shall follow the regulations set forth by the governing EC/IRB.

10.14.5 **Investigator Withdraws Subject**

No subjects should be withdrawn by investigators unless compelling medical justification is present. It is recommended investigators discuss any withdrawals with the study team prior to withdrawing subjects. If an Investigator Withdrawal is necessary, the following data should be collected prior to subject withdrawal if possible:

- Reason for subject withdrawal

11 Risks and Benefits

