12.3 Processing Updates and Resolution

For any changes in status of a previously reported AE or DD (i.e. change in actions taken, change in outcome, change in relatedness), information needs to be updated on, or added to the original AE or DD form. All AEs must be followed until the AE has been resolved, is unresolved with no further actions planned, the subject dies or exits the study, or until study closure, whichever occurs first.

In the event that a subject is exited from the study prior to study completion, all efforts should be made to continue following the subject until all unresolved system or procedure related AEs, as classified by the investigator, are resolved, or determined to be unresolved with no further actions planned. At the time of study exit, all collected adverse events that are unresolved must be reviewed and an update to the original AE must be reported.

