7.2 General Methodology

All statistical analyses will be performed using Statistical Analysis Software (SAS) for Windows (version 9.1 or higher) or other widely accepted statistical or graphical software. Subject data listings and tabular and graphical presentations of results will be provided.

All analyses will be based on “intent to treat” (ITT) principle, unless otherwise specified. For clinical events, the numerator of the event rate will be the number of “ITT” subjects having an event by the time of interest. The denominator will be the number of subjects who either have an event by the time of interest or have follow-up information beyond the lower window of the follow-up.

The Clinical Study Report will be available for the primary endpoint and for secondary endpoints annually through study close-out at 3 years.

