7.4 Handling of Missing, Unused, and Spurious Data and Dropouts

Every effort will be undertaken to minimize missing data. In time-to-event outcomes, drop-outs will be censored at the time of discontinuation, consistent with the Kaplan-Meier approach. Unless otherwise specified, no statistical techniques will be used to impute missing data for continuous or categorical characteristics and outcomes. The number of subjects included in each analysis will be reported so that the reader can assess the potential impact of missing data.

Screening and acceptance testing of these data will be carried out in accordance with Data Management Plan. To this end, all data involved in the determination of endpoints will be screened for missing and unusual values. Any missing data that affect the ability to determine or analyze any endpoint will be queried by Data Management for confirmation of irretrievability. Unusual values, such as outliers, will also be queried, and if confirmed, will be used as recorded.

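### Events after a study exit for safety or lack of effectiveness have no stated route into the study rates; the exposure lies mainly in the secondary, XLV and 24/36-month results

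*Protocol*

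**What the plan says.** Protocol 10.14.1 sets three rules for a subject who exits.

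- Collection stops: "Upon exiting from the study, no further study data will be collected, or study visits will occur for the subject".
- Analysis runs to that point: "All data available through the time of the subject's exit will be used for analysis".
- For a discontinuation because of safety or lack of effectiveness, "the subject shall be asked to be followed for collecting safety data outside the clinical investigation".

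Two other protocol sections bear on this. Section 10.14 allows a lesser step than exit: "Subjects may decide to withdraw from study follow up visits/contacts but consent to continue to allow data collection from their medical records". Section 12.3, on subjects who exit early, says "all efforts should be made to continue following the subject until all unresolved system or procedure related AEs" have settled.

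On analysis, SAP 7.2 counts a subject in the denominator of an event rate if the subject had the event by the time of interest or is among those who "have follow-up information beyond the lower window of the follow-up". SAP Appendix II puts the lower window limits at days 330, 690 and 1050 for 12, 24 and 36 months (360, 720 and 1080, each minus 30). SAP 7.4 says that in time-to-event outcomes "drop-outs will be censored at the time of discontinuation", and imputes nothing unless otherwise specified. SAP 7.9.1.1 and 7.9.1.3 do specify otherwise for 12-month TLF (Primary) and TVF (Bifurcation): subjects who leave event-free before day 330 enter a multiple imputation and a tipping-point analysis.

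**The concern.** Leaving because of a safety problem or a poor result is itself information about later risk. If such a subject's later events are not study data, the loss is informative, and its likely direction favours the device. Censoring at discontinuation assumes that leaving carries no such information.

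The stent is permanent. The protocol glossary starts very late stent thrombosis after 1 year and lets possible stent thrombosis depend on unexplained deaths up to the end of follow-up. An early exit shortens the observation of exactly these outcomes.

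The rules are also uneven. Under 10.14.3, a subject who cannot be reached is pursued throughout the 36 months, with a recommended check of death databases, and is not called lost until the 36-month window closes. A subject who leaves for a safety reason can be exited at once, and any later information is placed outside the study.

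**Working it through.** **1. Where an event goes, by timing**

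- *Before exit.* It is analysed (10.14.1), and under SAP 7.2 the subject stays in numerator and denominator for that endpoint. A clinically driven TLR that prompts exit already counts as TLF and TVF.
- *After exit, subject event-free at an exit before day 330.* The subject leaves both numerator and denominator of the 12-month rate. In the Primary and Bifurcation Cohorts, SAP 7.9.1 then imputes or varies the missing TLF or TVF status. The imputation covariates do not include the reason for exit, and neither analysis uses an outcome observed after exit. The Primary and XLV Cohorts also have a survival analysis, in which the subject is censored.
- *After exit, any other endpoint or time point.* A subject with TLR at month 5 who then exits counts in TLF. The same subject drops out of the stent thrombosis, cardiac death and TVMI denominators from 12 months on, unless one of those events also came before exit. No imputation or tipping-point analysis is specified for these endpoints, for the XLV Cohort, or for 24 and 36 months.

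**2. The plan's own figures**

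Inputs from protocol 14.2 and 14.5 are a one-sided alpha of 0.05 and success if the exact binomial upper 95% limit is below the goal. With x events in n subjects, the limit is the 95th percentile of Beta(x+1, n−x). Power is P(X ≤ c) for X ~ Binomial(n, true rate), where c is the largest passing count.

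| | Primary | Bifurcation |
|---|---|---|
| Evaluable n | 369 | 180 |
| Goal | 17.5% | 24.5% |
| Assumed true rate | 11.3% | 16.3% |
| Largest passing count c | 52 (limit 17.42%) | 34 (limit 24.34%) |
| Computed power | 95.9% | 85.1% |
| Stated power | 96% | 85% |

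Both stated powers reproduce.

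**3. How many unseen events would matter at 12 months**

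The documents give no number of such exits, so k is an assumption. The starting points are the expected counts, 0.113 × 369 ≈ 42 and 0.163 × 180 ≈ 29. Add k exited subjects to n and their unseen events to x.

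| Assumption | Primary: rate, upper limit | Bifurcation: rate, upper limit |
|---|---|---|
| k = 0 | 42/369 = 11.4%, 14.5% | 29/180 = 16.1%, 21.3% |
| k = 4, all with events | 46/373 = 12.3%, 15.5% | 33/184 = 17.9%, 23.2% |
| k = 10, half with events | 47/379 = 12.4%, 15.5% | 34/190 = 17.9%, 23.1% |
| k = 20, half with events | 52/389 = 13.4%, 16.5% | 39/200 = 19.5%, 24.7% (missed) |
| First k to miss, all with events | k = 13: 55/382 = 14.4%, 17.7% | k = 7: 36/187 = 19.3%, 24.6% |

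One exit fewer still passes: 54/381 has a limit of 17.45%, and 35/186 a limit of 24.16%.

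**4. Rare secondary endpoints**

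For scale only, assume a 36-month stent thrombosis rate of 1%. Over 410 + 100 + 185 = 695 subjects that is about 7 events. Losing 1 or 2 of them understates the count by 1/7 = 14% or 2/7 = 29%. Neither the 1% nor the number lost comes from the documents.

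**The case against.** The strongest reply is that the primary analyses are already guarded and the group may be close to empty.

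- SAP 7.9.1 addresses event-free dropouts before day 330. Its tipping-point analysis asks how many missing outcomes could be events with the goal still met, which covers the pessimistic case. This stands for 12-month TLF and TVF in the Primary and Bifurcation Cohorts. It does not reach the other outputs.
- The stent is implanted once, so there is no continuing treatment to stop. Safety or lack of effectiveness is not a separate item in the exit list of 10.14.1. Investigator withdrawal needs a compelling medical reason (10.14.5), and subjects are urged to stay. This stands: the number may be very small.
- Section 12.3 concerns settling adverse events already reported, not finding new endpoint events. That largely stands. Continued follow-up after exit still sits uneasily with "Upon exiting from the study, no further study data will be collected", but this is a tension to reconcile and not a flat contradiction.

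A reader might infer that the sponsor will hold these events and omit them from every rate. The documents do not support that. The subject is only asked, no text says the data reach the sponsor, and events before exit are counted. Exclusion of later events is the plain reading of 10.14.1, but SAP 7.10, which summarises all site-reported and CEC-adjudicated adverse events, leaves some doubt.

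A reader might also infer that one uncounted event can reverse the Bifurcation result. That holds only when the observed count is exactly 34 of 180 (35 of 180 gives a limit of 24.94%), as at the boundary of any threshold test.

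**Conclusion.** The point holds in a limited form. Under 10.14.1, events after an exit for safety or lack of effectiveness have no stated route to the CRF, the CEC or the rates of SAP 7.2 and 7.4, although the exit reason is related to outcome. The main exposure is the secondary endpoints (stent thrombosis, cardiac death, TVMI), the XLV Cohort and the 24- and 36-month rates, where events may be few and no imputation or tipping-point analysis is planned.

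The documents do not support a claim that the primary conclusions are at serious risk. From the expected counts, a reversal needs 7 (Bifurcation) or 13 (Primary) exits that all had unseen events. If half had events, 10 exits change neither result, and 20 change only Bifurcation. These figures assume that the evaluable numbers and expected rates of the sample-size sections hold. The number of exits and their later risk are assumptions throughout.

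**What to change.** Reconcile protocol 10.14.1 with 10.14 and 12.3. The change concerns data handling only and leaves the permitted reasons for exit as they are.

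1. Unless consent for data use is withdrawn, a subject who stops visits because of safety or lack of effectiveness moves to the record-based collection that 10.14 already allows, within the study through 36 months.
2. Vital status, MI, stent thrombosis and revascularization found this way are entered on the CRF and sent to the CEC.
3. SAP 7.2 and 7.4 state that these events enter the ITT numerators and denominators, and that subjects followed this way are not censored at discontinuation.
4. The number who exit for this reason is reported by cohort. SAP 7.1.1 already summarises reasons for discontinuation, but the exit list of 10.14.1 needs a way to record this one.

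The cost is a few sentences in the protocol and one or two in the SAP. The consent wording must cover continued use of the data, and observed event rates may rise slightly.

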11.1 Potential Risks

The risks associated with using this device are related to the drug, the stent materials and risks associated with standard percutaneous coronary diagnostic and treatment procedures.

Potential risks may also be referenced to in the *Instruction For Use* document.

11.1.1 **Zotarolimus**

Subjects' exposure to zotarolimus is directly related to the total amount of stent length implanted. The actual side effects/complications that may be associated with the use of zotarolimus are not fully known.

The adverse events that have been associated with zotarolimus in humans include but are not limited to:

- Anemia
- Circumoral paresthesia
- Diarrhea
- Dry Skin
- Headache
- Hematuria
- Infection
- Injection site reaction
- Pain (abdominal, arthralgia)
- Rash

11.1.2 **BioLinx Polymer Coating**

The types of risks of the BioLinx polymer coating are expected to be no different than those of other stent coatings. These risks may include but are not limited to the following:

- Allergic reaction
- Focal inflammation at the site of stent implantation
- Restenosis of the stented artery

11.1.3 **Percutaneous Coronary Diagnostic and Treatment Procedures**

Other risks associated with using this device are those associated with percutaneous coronary diagnostic (including angiography and IVUS) and treatment procedures. These risks (in alphabetical order) may include but are not limited to the following:

- Abrupt vessel closure
- Access site pain, hematoma or hemorrhage
- Allergic reaction (to contrast, antiplatelet therapy, stent material, or drug and polymer coating)
- Aneurysm, pseudoaneurysm, or arteriovenous fistula (AVF)
- Arrhythmias, including ventricular fibrillation
- Balloon rupture
- Bleeding
- Cardiac tamponade
- Coronary artery occlusion, perforation, rupture, or dissection
- Coronary artery spasm
- Death

- Embolism (air, tissue, device, or thrombus)
- Emergency surgery: peripheral vascular or coronary bypass
- Failure to deliver the stent
- Hemorrhage requiring transfusion
- Hypotension / hypertension
- Incomplete stent apposition
- Infection or fever
- Myocardial infarction (MI)
- Pericarditis
- Peripheral ischemia / peripheral nerve injury
- Renal Failure
- Restenosis of the stented artery
- Shock / pulmonary edema
- Stable or Unstable angina
- Stent deformation, collapse, or fracture
- Stent embolization
- Stent migration or embolization
- Stent misplacement
- Stroke / transient ischemic attack (TIA)
- Thrombosis (acute, sub-acute, late, or very late)

